7.2 Assignment of Groups

Enrollment **in the main phase** occurs with collection of baseline study samples on study Day -14. Randomization will occur prior to enrollment, prior to or on study Day -14. Randomization of the subjects in Arm 1 and 3a will occur first as these subjects will be enrolled first. Randomization of Arm 2 and 3b will occur together later prior to enrollment. If a subject was randomized into group 1 or 3a but was not vaccinated, they may be randomized into groups 2 and 3b if still eligible.

If a subject withdraws from the study after randomization, they can be replaced by another subject at random if withdrawal happens prior to receipt of first vaccination. Once a subject has received their first vaccination, they cannot be replaced.

For the booster phase, enrollment will occur at the receipt of the first dose of artemether/lumefantrine prior to vaccination. Enrolled subjects cannot be replaced.

During the study, the list linking randomization numbers to study product (PfSPZ Vaccine or control) will be made available only to the study statistician and associated team members, pharmacy team/syringe preparers (at the start of the study), independent safety monitor (if needed to review as outlined in **Section 11.15.2**), and DSMB chair (if needed for closed session unblinded review). On vaccination days, the vaccines associated with each randomization number will be obtained from the pharmacist.

To ensure proper identification of study subjects, following subject enrollment all subjects will receive an identification card with their photo on it to present at the clinic with each study visit.

7.3 Detailed Study Procedures

Detailed study procedures are outlined in **Appendix A** of the protocol.

8 STUDY PROCEDURES/EVALUATIONS

8.1 Photographs of Rash or Injection Site Reactions

If a subject develops a rash or injection site reaction, photographs may be taken by the investigators. These photographs will not include the subject's face or any identifying scars, marks, or tattoos.

8.2 Clinical Laboratory Testing

Using standard techniques, the clinical laboratory will perform the following tests:

1. Complete blood count (CBC) plus white blood cell (WBC) differential and platelet count
 - The following CBC parameters will be assessed for safety throughout the trial: WBC, absolute neutrophil count (ANC)/absolute granulocyte count (AGC), hemoglobin (Hb), and platelet count.
2. Serum creatinine (Cr)
3. Alanine aminotransferase (ALT)
4. HBsAg test (can include rapid diagnostics, ELISA, PCR if indicated) (at screening only in the main phase. For the booster phase, ONLY if clinically indicated)
5. HCV test (can include rapid diagnostics, ELISA, PCR if indicated) (at screening only in the main phase. For the booster phase, ONLY if clinically indicated)
6. HIV test (can include rapid diagnostics, ELISA, Western Blot if indicated) (at screening only in the main phase. For the booster phase, ONLY if clinically indicated)
7. Urine dipstick and/or Urinalysis (at screening for the main and booster phases only)
8. Urine and/or serum pregnancy testing (β -hCG)

Additional clinical testing includes the following but will be completed retrospectively by other laboratories as noted below:

1. Hemoglobinopathy testing - testing for normal adult hemoglobin (HbAA), hemoglobin c trait (HbCC), hemoglobin sickle cell trait (HbAS), hemoglobin sickle cell disease (HbSS)

8.3 Electrocardiogram

8.3.1 Electrocardiogram for the Study

Electrocardiograms (12-lead ECGs) will be performed during screening in the main phase and as needed throughout the study and will be read by the study site physician in Mali, a Mali cardiologist or NIH study cardiologist or their representative. Subjects with QT interval (QTc) > 460 ms may be excluded as Coartem may prolong QTc. Subjects with clinically significant abnormalities will also be excluded from the study.

8.4 Malaria Diagnostics

8.4.1 Malaria Blood Smears

The gold standard for malaria diagnosis and evaluation of VE endpoints is the detection of malaria parasites on Giemsa-stained thick blood films. Blood films will be prepared at the specified time points or when clinically indicated and will be examined by technicians with a documented experience in slide reading following the SOP established for malaria slide reading

within the MRTC (Guindo et al., 2012), and in consideration of the modifications suggested for CHMI trials (Laurens et al., 2012). Slides are considered positive if at least two unambiguous *P. falciparum* parasites per slide are identified and confirmed by a second microscopist. Positive results will be reported promptly to the study Principal Investigator or designee.

Thick blood smears will be prepared from the blood remaining in the IV cannula, or (at time points when no IV blood collection is planned) from a finger prick sample. The smears will be examined microscopically.

Thick blood smears will be used for diagnosis throughout the study.

8.4.2 Malaria qPCR

While detection of parasites on thick blood smears remains the most common primary endpoint in human challenge trials, both PCR- and nucleic acid sequence-based amplification (NASBA)-based methods have been increasingly used to support blood smear data in malaria vaccine trials (M. Walther et al., 2005; M. Walther et al., 2006). These research molecular assays have significantly increased sensitivity for detection of *P. falciparum* blood-stage infection approaching 20 parasites/mL, often resulting in diagnosis 2-4 days earlier than by paired thick blood smears (Hermsen et al., 2001; Schneider et al., 2004; M. Walther et al., 2005).

Quantification of parasite density by these methods allows evaluation of parasite growth curves for assessing the utility of partially-effective vaccine candidates. LMIV has also developed a research qPCR that detects 18s of *P. falciparum* with a detection limit of at least 20 parasites/mL that will be used during the study for comparison to traditional thick blood smears.

P. falciparum qPCR may be performed from all scheduled visits with a malaria blood smear noted (see **Appendix A**) to capture infections that remain below the detection limit for microscopy. For subject convenience, a finger prick sample can be used for both preparation of the microscopy slide and for DNA preservation.

8.5 Unscheduled Blood Smear Positive Visits

Each time a subjects has detected *P. falciparum* malaria parasites on thick blood smear (whether or not they were symptomatic; scheduled or unscheduled visits), he/she will be asked to the clinic to provide an additional blood sample within 24 hours of the clinic visit (the next calendar day) for the following as seen in **Appendix A**:

- 0.5 mL ethylene diamine tetraacetic acid (EDTA) microtainer: for whole blood ex-vivo assays if sample not obtained within the last two days of the positive blood smear .(For the booster phase, only collect if the sample has not been obtained within the last 7 days).
- 4 mL EDTA tube: to obtain RNA and DNA for the study of host and parasite transcriptome (RNA) and parasite genotype (DNA) and to obtain plasma for proteomics studies if sample not obtained within the last 28 days of the positive blood smear
- 0.5 mL for qPCR if sample not obtained within the last two days of the positive blood smear (For the booster phase, NOT required)

Note: if a blood smear is positive for *P. falciparum*, documentation in a smear positive CRF is required whether these additional samples were collected or not.

8.6 Immunologic Laboratories

As indicated in the objectives, assays will be conducted to assess immunogenicity in addition to safety as described above. Laboratory assays to assess immune response to PfSPZ Vaccine will be performed at the LMIV, NIAID, NIH, Sanaria Inc, and NIH Center for Human Immunology according to standard laboratory procedures.

These assays include:

1. Binding ELISA for antibodies to *P. falciparum* liver stage and blood stage antigens (which includes but not limited to: CSP, sporozoite surface protein 2, liver stage antigen 1, erythrocyte binding antigen 175, merozoite surface protein 1, merozoite surface protein 5, and exported protein 1 [PfCSP, PflSA-1, PfEBA-175, PfMSP-1, PfMSP-5, malaria protein EXP-1])
2. (IFN- γ) ELISPOT assay and multi-parameter flow cytometry with intracellular cytokine staining on peripheral blood mononuclear cells in *P. falciparum* liver- stage antigens (CSP, LSA-1) and PfSPZ
3. B and T cells studies to analyze immunologic responses

Sanaria, Inc. will also assess antibodies to whole PfSPZ by immunofluorescence assay (IFA) and inhibition of sporozoite invasion assay (ISI) and to asexual erythrocytic stage parasites by IFA as described (Epstein et al., 2011; Seder et al., 2013) and also by protein microarrays (Antigen Discovery Inc).

In addition, using plasma, sera, peripheral blood mononuclear cells, or their component parts (e.g., purified IgG), Naval Medical Research Center will perform assays of humoral and cellular immunity that may be associated with protective activity.

Laboratory assays to assess immune responses to novel pre-erythrocytic antigens will be performed in the PEVA Consortium laboratories at the LMIV, NIAID, and NIH according to standard laboratory procedures. The target proteins are novel antigens that confer protection against liver stage malaria in rodent malaria models (*P. yoelii*, *P. berghei*) according to vaccination studies conducted by Seattle BioMed and LMIV. The novel antigens to be used for these laboratory assays include PFL1995c, PFE0305w, LISP1 (PF14_0179), SAP1 (PF11_0480), MAL7P1.164, PF14_0113, using the identifiers in the PlasmoDB database (www.plasmodb.org). These antigens were initially selected on the basis of their gene expression during early liver stage development of *P. falciparum*, and preliminary testing shows that these antigens are immunologically recognized by individuals previously exposed to *P. falciparum*. The potential utility of these antigens as pre-erythrocytic vaccines has been supported by animal studies, wherein orthologues of these genes incorporated in DNA vaccines induce protective immunity in mice that significantly reduces the liver stage development of *P. berghei* and *P. yoelii* parasites. The assays included in this study can confirm that individuals receiving CVac with PYR develop immune responses to pre-erythrocytic antigens and can provide additional data by which to assess the potential for these antigens to be developed as subunit vaccines to prevent infection. The long-term objective of the PEVA consortium is to identify antigens that individually, or in combination with CSP or other antigens, will induce a high level of pre-erythrocytic immunity that is protective against *P. falciparum*.

The assays to be performed include:

1. Binding ELISA for antibodies to *P. falciparum* pre-erythrocytic antigens (PFL1995c, PFE0305w, LISP1 (PF14_0179), SAP1 (PF11_0480), MAL7P1.164, PF14_0113)

2. IFN- γ ELISPOT/Intracellular cytokine staining (ICS) assay on peripheral blood mononuclear cells in *P. falciparum* pre-erythrocytic antigens (PFL1995c, PFE0305w, LISP1 (PF14_0179), SAP1 (PF11_0480), MAL7P1.164, PF14_0113)

8.7 Transcriptomic analysis

Whole genome transcriptional profiling will be performed to explore possible gene expression profiles or pathways that predict optimal responses to vaccination. Gene expression profiling following vaccination will allow the predictive capacity of eventual protected and unprotected vaccinees, and thus will assist in defining the correlates of protection induced by vaccination. Transcriptional analyses will be performed on whole blood collected as outlined in **Appendix A**. Blood will be collected via venous puncture and placed in PAXGene tubes to preserve RNA integrity until the RNA is extracted. The molecular profiling encompasses the identification of RNA transcripts present in all humans, which are induced or repressed after each vaccination. This does not represent genetic testing of individuals or their DNA.

9 RESEARCH USE OF STORED HUMAN SPECIMENS

Intended Use: Samples and data collected under this protocol will be used to study malaria and related diseases and possible adverse reactions to vaccination.

Storage: Access to stored research samples will be limited using either a locked room or a locked freezer. Temporary storage of samples collected in Mali, prior to shipment to LMIV, may occur at the Core Immunology Laboratory or the MRTC CAP laboratory. Samples will be stored at the LMIV in Rockville, MD or at LMIV's designated repository, Thermo Scientific, Rockville, MD, with the exception of retention specimens which may be kept at the MRTC in Mali for quality control. Samples and data will be stored using codes assigned by the investigators or their designees. Data will be kept in password-protected computers. Only investigators or their designees will have access to the samples and data.

Tracking: Samples will be tracked using a sample-tracking software program, e.g., Freezerworks.

Disposition at the Completion of the Protocol: In the future, other investigators (both at the NIH and outside) may wish to study these samples and/or data. In that case, Institutional Review Board (IRB) approval must be sought prior to any sharing of samples. Any clinical information shared about the sample with or without patient identifiers would similarly require prior IRB approval.

At the completion of the protocol (termination), samples and data will either be destroyed or, after IRB approval, transferred to another existing protocol.

Reporting the Loss or Destruction of Samples/Specimens/Data to the IRB: Any loss or unanticipated destruction of samples (for example, due to freezer malfunction) or data (for example, misplacing a printout of data with identifiers) that meets the definition of Protocol

Deviation and/or compromises the scientific integrity of the data collected for the study, will be reported to the NIAID IRB.

Consent to allow long term storage of study samples is a part of the inclusion criteria for this study. However, if a subject decides following enrollment not to have their samples stored, the PI or designee will destroy all known remaining samples and report this destruction to the subject and the NIAID IRB and Faculty of Medicine, Pharmacy and Odonto-Stomatology Ethics Committee (FMPOS EC). This decision will not affect the subject's continued participation in this protocol or any other protocols supported by the NIH.

10 DATA SHARING PLAN

In NIH's view, all data should be considered for data sharing. Data should be made as widely and freely available as possible while safeguarding the privacy of subjects, and protecting confidential and proprietary data. We recognize that the public dissemination of our scientific results can facilitate the creation of collaborative efforts with domestic and international collaborators. Furthermore, we recognize that the proposed project may result in novel ideas for new methods, technologies, and data that could benefit the entire research community. Therefore, final research data will be shared openly and timely in accordance with the most recent NIH guidelines (http://grants.nih.gov/grants/policy/data_sharing/) while being mindful that the confidentiality and privacy of participants in research must be protected at all times. Timelines for distribution of data will vary depending on any required restrictions in accordance with federal and/or institutional policies and guidelines. In general, we expect de-identified data will be available through NIH-funded or approved public repository, speaking engagements and publications, presentations at scientific symposia and seminars. Effort will be made to publish our research findings in scientific journals. All final peer-reviewed manuscripts that arise from this proposal will be submitted to the digital archive PubMed Central. For tools, reagents, data and model organisms generated by the proposed study, pending third parties' rights, LMIV will transfer materials to outside researchers in both the private and public sectors under a Material Transfer Agreement or Research Collaboration Agreement.

11 ASSESSMENT OF SAFETY

11.1 Documenting, Recording, and Reporting Adverse Events

At each contact with the subject, information regarding adverse events will be elicited by appropriate questioning and examinations and will be:

- immediately documented in the subject's medical record/source document,
- recorded on the Adverse Event Case Report Form (AE CRF) or electronic database, and
- reported as outlined below (e.g., IND sponsor, IRB, FDA).

A study clinician will be available during the study period and will be available to the study subjects at all times. Should a subject call a study clinician to report an AE, it will be discussed with the PI and documented, recorded, and reported appropriately.

11.2 Definitions

Adverse Event (AE): An AE is any untoward or unfavorable medical occurrence in a human subject, including any abnormal sign (e.g., abnormal physical exam or laboratory finding), symptom, or disease, temporally associated with the subject's participation in the research, whether or not considered related to the research.

Adverse Reaction (AR): An AR is an adverse event that is caused by an investigational agent (drug or biologic).

Suspected Adverse Reaction (SAR): A SAR is an adverse event for which there is a reasonable possibility that the investigational agent caused the adverse event. 'Reasonable possibility' means that there is evidence to suggest a causal relationship between the drug and the adverse

event. A suspected adverse reaction implies a lesser degree of certainty about causality than adverse reaction which implies a high degree of certainty.

Serious Adverse Event (SAE): A SAE is defined as an AE that results in any of the following outcomes:

- death
- life threatening (i.e., an immediate threat to life)
- inpatient hospitalization or prolongation of an existing hospitalization
- persistent or significant incapacity or substantial disruption of the ability to conduct normal life functions
- congenital anomaly/birth defect
- medically important event

Medical and scientific judgment will be exercised in deciding whether expedited reporting is appropriate in other situations, such as important medical events that may not be immediately life threatening or result in death or result in hospitalization but may jeopardize the subject or may require intervention to prevent one of the other outcomes listed above.

Unexpected Adverse Event: An AE is considered unexpected if it is not listed in the Investigator's Brochure (IB) or Package Insert (for marketed products) or is not listed at the specificity or severity that has been observed. It is the responsibility of the IND sponsor to make this determination.

Serious and Unexpected Suspected Adverse Reaction (SUSAR): A SUSAR is a SAR that is both serious and unexpected.

Unanticipated Problem (UP): An UP is any event, incident, experience, or outcome that is

1. unexpected in terms of nature, severity, or frequency in relation to
 - a. the research risks that are described in the IRB-approved research protocol and informed consent document, IB, or other study documents; and
 - b. the characteristics of the subject population being studied; and
2. possibly, probably, or definitely related to participation in the research; and
3. places subjects or others at a greater risk of harm (including physical, psychological, economic, or social harm) than was previously known or recognized.

Unanticipated Problem that is not an Adverse Event (UPnonAE): An UPnonAE is an UP that does not fit the definition of an adverse event, but which may, in the opinion of the investigator, involve risk to the subject, affect others in the research study, or significantly impact the integrity of research data. Such events would be considered a non-serious UP. For example, we will report occurrences of breaches of confidentiality, accidental destruction of study records, or unaccounted-for study drug.

New Onset of Chronic Illness (NOCI): A NOCI is defined as a diagnosis of a new medical condition that is chronic in nature, including those potentially controllable by medication (e.g., diabetes, asthma). Any NOCI will be recorded in the same manner as unsolicited AEs.

Protocol Deviation: Any change, divergence, or departure from the IRB approved study procedures in a research protocol. Protocol deviations are designated as major or minor.

Major Deviations - Deviations from the IRB approved protocol that have, or may have the potential to, negatively impact, the rights, welfare or safety of the subject, or to substantially negatively impact the scientific integrity or validity of the study.

Minor Deviations - Deviations that do not have the potential to negatively impact the rights, safety, or welfare of subjects or others, or the scientific integrity or validity of the study.

Noncompliance: Failure of investigator(s) to follow the applicable laws, regulations, or institutional policies governing the protection of human subjects in research or the requirements or determinations of the IRB, whether intentional or not

11.3 Investigator Assessment of Adverse Events

If a diagnosis is clinically evident (or subsequently determined), the diagnosis rather than the individual signs and symptoms or lab abnormalities will be recorded as the AE.

All solicited (see **Table 6** below) and unsolicited AEs will be recorded through Day 7 after each injection. Injection site reactions will be assessed until Day 7 after injection (PfSPZ Vaccine or normal saline) or until resolved.

After the periods specified above only unsolicited AEs, SAEs, UPs, and NOCIs will be recorded.

Table 6: Solicited Adverse Events

Laboratory adverse events¹	
Hemoglobin (decreased hemoglobin)	Platelet count (thrombocytopenia or thrombocytosis)
WBC (leukopenia or leukocytosis)	Creatinine (Cr) (increased Cr)
ANC (neutrophil count decreased) or AGC (granulocyte count decreased)	ALT (increased ALT)
Local reactogenicity (secondary to PfSPZ Vaccine/normal saline) – through Day 7 post injection	
Injection site pain/tenderness	Injection site induration
Injection site erythema/redness	Injection site swelling/edema
Injection site pruritus	Injection site bruising
Systemic reactogenicity (secondary to PfSPZ Vaccine/normal saline) – through Day 7 post injection	
Rash	Urticaria
Generalized pruritus	Generalized Edema
Headache	Fever or feverish
Chills	Malaise/Fatigue
Myalgia	Arthralgia
Sweats	Diarrhea
Back Pain	Chest Pain (non-musculoskeletal)
Nausea/Vomiting	Abdominal Pain

¹ Note absolute lymphocyte counts will be capture on CRFs for use for research assessments. If clinically significant changes as determined by PI, these may also be reported as AEs as noted below.

Any laboratory abnormalities (other than those specified as safety labs in the protocol as defined by the values in the toxicity table) should be reported as AEs if they require intervention. Interventions include, but are not limited to, discontinuation of treatment, dose reduction/delay, additional assessments, or concomitant treatment. In addition, any medically important laboratory abnormality may be reported as an adverse event at the discretion of the investigator. This could include a laboratory result for which there is no intervention, but the abnormal value suggests a disease or organ toxicity. In addition, similar to solicited AEs, all laboratory AEs as defined in **Appendix C**, will be collected and graded for severity through 7 days after each vaccination until resolved.

The Investigator will assess all AEs with respect to **Seriousness** (criteria listed above), **Severity** (intensity or grade), and **Causality** (relationship to study agent and relationship to research) according to the following sections in the protocol.

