1.6 Rationale for assessing various vaccination schedules

A number of PfSPZ Vaccine studies are ongoing to determine a highly effective vaccine schedule. There is ample evidence that the timing of each vaccine plays an important role in the development of protective immunity. A recent study in malaria naïve subjects, MAVACHE study described in **Section 1.5**, suggests that a condensed regimen of 0, 1 and 4 weeks injections may lead to equal or higher protective efficacy.

This condensed vaccine regimen was also found to be safe and well tolerated. Among the six subjects, during the time from first injection and prior to CHMI, there was a total of 82 AEs, 74% of which were determined related to the study. There was a total of 3 Grade 3 AEs in two subjects which were also thought to be related to the study. The first subject had lymphopenia one day after 3rd vaccination. The second subject had 2/3 Grade 3 AEs; lymphopenia 12 days after 2nd vaccination and fever two days after 3rd vaccination. No SAE was observed.

The safety profile and protective efficacy of this regimen are encouraging. Since our goal at LMIV is to understand the immune response to vaccine candidates, this proposed study will also evaluate a condensed regimen of 0, 1, and 4 weeks in a field setting to assess whether this regimen is safe and tolerable in this population. We will also evaluate the protective efficacy observed with this condensed regimen and explore the immune response to vaccination.

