11.10 Pausing Criteria for the Study

The PI will closely monitor blinded study data as they become available and will make determinations regarding the presence and grading of AEs. The AEs will be evaluated with regard to the known complications associated with administration of vaccine components. If a dose of vaccine is considered unacceptably reactogenic (as described in the following criteria), the study will be paused. No new enrollments and no further vaccinations will be administered by the investigators until reviewed by the DSMB and study IND sponsor. A report of DSMB recommendations will be submitted to the IRBs. The following criteria will be used to define unacceptable reactogenicity of the malaria vaccine (AEs that are possibly, probably, or definitely related to the vaccine will be considered "Related" and will be summarized as such):

1. One or more subjects experience an SAE as defined in **Section 11.4.2** of this protocol that is determined to be possibly, probably, or definitely related to the vaccine or placebo or
2. One or more subjects experience a hypersensitivity reaction (e.g. anaphylaxis, diffuse urticaria) that is probably or definitely related to the vaccine or placebo; or
3. Any severe clinical illness occurs that is not explained by a diagnosis that is unrelated to injection; or

4. Thirty percent of subjects in any dose arm experience the same Grade 2 or higher laboratory abnormality (see **Appendix B**), or Grade 3 systemic AE that is determined to be possibly, probably, or definitely related to the injection (PfSPZ Vaccine or placebo) as defined in this protocol or
5. Ten percent of subjects in any arm experience Grade 3 or higher local reactogenicity; or
6. Any safety issue that the study PI or IND sponsor determines should pause the study.

The IRBs, the NIAID, the FDA, or other government agencies may discontinue the study at any time. Subsequent review of serious, unexpected, and related AEs by the DSMB or IRB, the IND sponsor, the FDA, and other regulatory authorities may also result in suspension of further administration of vaccine at the clinical site (or, in the case of the DSMB, a recommendation to the Sponsor that the study should be suspended). The FDA, other regulatory authorities, and the study sponsor(s) retain the authority to suspend additional enrollment and administration of vaccine for the entire study as applicable.

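### The lymphocyte count is recorded but not systematically scored for safety, although related Grade 3 lymphopenia was reported in two of six earlier recipients of the 0, 1, 4 week regimen

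*Combined protocol and SAP*

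**What the plan says.** Section 8.2 lists "Complete blood count (CBC) plus white blood cell (WBC) differential and platelet count", so a lymphocyte count is produced at every CBC. The next line narrows what counts as safety: "The following CBC parameters will be assessed for safety throughout the trial: WBC, absolute neutrophil count", followed by hemoglobin and platelets. Lymphocytes are not named.

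Table 6 in Section 11.3 lists six solicited laboratory parameters: hemoglobin, WBC, neutrophils or granulocytes, platelets, creatinine and ALT. Its footnote says "Note absolute lymphocyte counts will be capture on CRFs for use for research assessments" and continues: "If clinically significant changes as determined by PI, these may also be reported as AEs as noted below".

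The text below the table adds two routes for abnormalities outside the safety laboratories. They should be reported if they require intervention, and additional assessments count as intervention. Also, "any medically important laboratory abnormality may be reported as an adverse event at the discretion of the investigator".

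Appendix B gives a lymphocyte reference range of 1.3 to 4.4 x10^3/µL but no severity grades for it. Section 11.3.1 sends AEs that have no appendix row to Table 7, which grades by activity limitation and need for care.

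Section 1.6 reports three related Grade 3 AEs in two of six subjects given the 0, 1, 4 week regimen. Of these, "The first subject had lymphopenia one day after 3rd vaccination"; the second had "lymphopenia 12 days after 2nd vaccination and fever two days after 3rd vaccination".

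**The concern.** The safety of the two regimens is the primary objective (Section 2.1). For the newer regimen, most of the severe events that the protocol itself reports were lymphopenia. One would expect that parameter to be scored the same way in every subject. Instead it is assigned to research, and its route into the safety data depends on someone deciding that a value matters.

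Three things follow. The proportion of subjects with lymphopenia in each arm would reflect reporting habits as well as counts. An asymptomatic low count reported as an AE need not be Grade 3 under Table 7. The laboratory limb of pausing criterion 4 ("Thirty percent of subjects in any dose arm experience the same Grade 2 or higher laboratory abnormality") refers to Appendix B, which has no lymphocyte grade for it to act on.

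Section 1.7.1 already draws reassurance for the condensed schedule from AE proportions. The laboratory events it names are neutrophil, WBC, creatinine and platelet changes.

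**Working it through.** **The plan's own detection figure.** Section 13.2 gives a 90% probability of at least one AE among 70 subjects at a rate of 0.033. Check: 1 − (1 − 0.033)^70 = 1 − 0.967^70 = 0.9045. It reproduces. It assumes that every event is recorded as an AE.

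**The earlier cohort (Section 1.6).**
- Share of Grade 3 AEs that were lymphopenia: 2/3 = 67%.
- Subjects affected: 2/6 = 33.3%; exact (Clopper-Pearson) 95% CI 4.3% to 77.7%.
- Timing: one event on day 1 after dose 3, one on day 12 after dose 2. Section 11.3 collects and grades laboratory AEs through Day 7, so one of the two falls outside that window.

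**Effect of discretionary recording.** Take the lower confidence limit, r = 0.043, and let f be the fraction of events that reach the AE record. The documents give no value for f, so the range is an assumption. P(at least one recorded among 70) = 1 − (1 − r·f)^70:

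| f | P(at least one recorded) |
|---|---|
| 1.00 | 0.955 |
| 0.50 | 0.78 |
| 0.25 | 0.53 |
| 0.10 | 0.26 |

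**Can the graded white-cell rows stand in?** Appendix B: WBC reference range 3.6 to 9.0, Grade 1 decrease 2.5 to 3.3; neutrophil reference range 1.3 to 4.4 (all x10^3/µL).
- Illustration: neutrophils 3.5 + lymphocytes 0.4 + other cells 0.3 = WBC 4.2. Both graded parameters are normal while the lymphocyte count is far below 1.3.
- More generally, ignoring other cells, WBC stays at or above 3.4 with lymphocytes at 0.5 whenever neutrophils are at least 2.9 (0.5 + 2.9 = 3.4). With no lymphocytes at all, it does so whenever neutrophils are at least 3.4.

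So the WBC and neutrophil rows are not a reliable substitute.

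**Are there counts after Day 7?** The Appendix A booster tables are broken in the supplied text, so this is an inference from volumes. The Day 14 total is 21.5 mL. CBC 2 + ALT and creatinine 3 + qPCR 0.5 + smear 0.5 + humoral 5 + cellular 10 + ex vivo 0.5 = 21.5. That is consistent with a CBC on Day 14 after the booster. The supplied text contains no main-phase schedule.

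**The case against.** A reader might infer that the trial cannot see lymphopenia at all. The documents do not support that. The count is measured and kept, and Section 11.3 gives three routes to an AE: clinical significance, need for intervention (including further assessments) and medical importance. Table 7 supplies a fallback grade. Unsolicited AEs are recorded after Day 7, so a Day 12 event can be captured. A lymphopenia judged related would enter the related-AE comparison in Section 13.1.1, which also allows other concerning trends to be examined. Pausing criterion 6 covers any safety issue that the PI or sponsor identifies.

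Nor does the point reach the primary endpoint as worded. Section 4.1 names local and systemic AEs within 7 days and does not mention laboratory AEs. The link is to the safety objective, the solicited laboratory AEs and Section 13.1.1.

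It is also tempting to set 33% against the 30% pausing threshold. With an interval of 4% to 78% from six malaria-naive subjects, graded on a scale the documents do not give, that comparison says almost nothing. Section 1.7 states that all third doses were given in September 2018, so under this version no pausing rule could act on the 0, 1, 4 week series.

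Finally, blinding makes it unlikely that discretion favours one arm over its own control. All of this stands. None of it makes ascertainment systematic or based on the count: blinding limits differential bias, not under-recording.

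**Conclusion.** The point holds in a limited form. Lymphopenia is ascertained by judgement or intervention and graded by function, while the other main CBC parameters are solicited and graded by value. The reason to treat lymphocytes alike is in the protocol's own Section 1.6.

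The size is uncertain. The prior rate could lie anywhere from 4% to 78%. At its lower limit, the chance of recording at least one case in a 70-subject arm falls from 0.955 under complete recording to 0.53 if a quarter of events are reported, and that fraction is assumed. The evidence does not show that the condensed regimen causes lymphopenia in Malian adults. It shows that a statement of similar laboratory safety would not have tested this parameter evenly. The change is worth making; the gap does not undermine the trial.

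**What to change.** 1. Add to Section 13.1.1 a prespecified summary by arm, and a vaccine-versus-placebo comparison within each regimen (Arm 1 with 3a, Arm 2 with 3b), of the lymphocyte counts on the CRF. Do this for both phases. Report change from baseline, lowest value, and proportion below the 1.3 reference limit in Appendix B.
2. Use every scheduled CBC, including those after Day 7. Confirm the booster Day 14 CBC, and the main-phase draw days, against the intact schedules.
3. Amend the Table 6 footnote so that the count is used for safety as well as research, and add it to the safety parameters in Section 8.2.
4. Leave to the sponsor whether to add a graded row to Appendix B, where any cut-offs lie, and whether pausing criterion 4 should refer to it.
5. While editing Section 11.3, reconcile its pointer to Appendix C for laboratory AEs: Appendix C is the reference list, and the toxicity table is Appendix B.

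Cost: a short wording change and a little more analysis. No new blood is needed, and main-phase values can be summarised retrospectively. If the sponsor adds grades, some extra low-grade laboratory AEs will appear in all arms.
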